#### Saw bone simulation

After completing VR training, all participants were asked to implant the cup at a 60° inclination in sawbones and the femoral stem at 20° of anteversion. As mentioned, they performed one implantation following VR training and the other without VR training.

[figure not shown]
The sawbones had been reamed and prepared appropriately to accommodate the metal prostheses from the students steadily. The students did not perform any reaming to the sawbones. The same saw bone was used for several implantations but was replaced with a new one when it could no longer handle the implant properly. The cup inclination and stem version were evaluated using specific goniometers and assessment of photographs taken during implantation. During implantation in sawbones, a study assistant was present and was instructed to intervene only if the study participants requested assistance or could not progress through the task.

Upon completion of the VR-THAs, participants completed a survey focused on their interest in using VR simulations for surgical skills training and assessing potential negative consequences.

#### Power Analysis

After reviewing eight recent RCT studies on virtual reality simulation training, it was found that each study had an average of 14 to 28 participants and an effect size of 0.80 to 0.90. Previous studies have utilised specific scores to evaluate the impact of trauma or arthroplasty simulator training on actual performance in real-world scenarios. These evaluations were different from our measurements. To assess the necessary sample size for our study, we based on the first ten measurements of cup angle implantation from our medical students; the mean cup angle was 50.40 with a standard deviation of 18°. To detect a difference of 20 degrees of implantation

between two groups with a standard deviation of 18 degrees and with a two-sided alpha of 0.05 and power of 80%, at least 26 students were required in its group.

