#### Recruitment

This prospective randomised trial was approved by our Institutional Review Board (70/2023-15/02/2023). Eligible study participants included undergraduate medical students at our university with no previous surgical experience willing to participate. Exclusion criteria included a. postgraduate medical students b. prior experience in THA or general surgery, c. undergraduate students unwilling to participate.

One month before the planned VR-THA surgery session, all eligible medical students were invited to an information session regarding the study through the university's social media. The 101 medical students who fulfilled the inclusion criteria were voluntarily enrolled, providing informed consent.

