**Figure 1, Study Design**

### **Statistical Analysis Plan (SAP)**

The primary outcome was the mean implanted cup inclination and femoral stem anteversion difference between the VR and control groups. Other outcomes considered between groups included: a) the duration required to complete the task, b) the frequency of requesting assistance, and c) the number of errors made.

We used standard statistical methods to gather descriptive statistics. We conducted the Kolmogorov-Smirnov and Shapiro-Wilk tests to check whether the data followed a normal distribution. Our statistical tests were two-tailed, and we set the alpha level at 0.05. For continuous variables that were normally distributed, we used the two-sided independent sample t-test, while for those that weren't normally distributed, we used the Mann-Whitney U-test. We compared categorical data using the chi-square test. To determine if using VR had an impact on a student's task performance, a paired t-test was conducted to compare their outcomes with and without VR. We performed all statistical analyses using SPSS software (IBM, version 27.0).

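### The sample size inputs (20°, SD 18°, two-sided 0.05, 80% power) give 13 or 14 students per group, not the 26 stated

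*Combined protocol and SAP*

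**What the plan says.** The Power Analysis section first mentions earlier simulation trials with effect sizes of 0.80 to 0.90. It then sets them aside because of how they measured performance: "These evaluations were different from our measurements". The calculation is instead said to rest on the first ten cup angles measured in this study (mean 50.40, SD 18°).

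The inputs follow: "To detect a difference of 20 degrees of implantation" "between two groups with a standard deviation of 18 degrees". The result is: "with a two-sided alpha of 0.05 and power of 80%, at least 26 students were required in its group". No dropout allowance, multiplicity adjustment or other inflation is given.

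On analysis, the SAP states: "For continuous variables that were normally distributed, we used the two-sided independent sample t-test". Its fallback for other continuous data is given as "normally distributed, we used the Mann-Whitney U-test". On the significance level it says "we set the alpha level at 0.05". The Recruitment section reports the number who entered: "The 101 medical students who fulfilled the inclusion criteria were voluntarily enrolled".

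**The concern.** A 20° difference with an SD of 18° is a standardised effect of 20/18 = 1.11, which is large. An effect of that size needs far fewer than 26 per group for 80% power, so the result does not appear to belong to the inputs printed beside it.

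What is at stake is whether the statement can be reproduced and read correctly. A reader would take 26 per group as the size at which 20° is detected with 80% power. Someone planning a similar study from this sentence would either recruit almost twice what the inputs require or infer the wrong target difference. The adequacy of this trial for 20° is not in question.

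**Working it through.** **Inputs.** From the Power Analysis section: difference 20°, SD 18°, two-sided alpha 0.05, power 80%. From the SAP: independent-sample t-test at alpha 0.05. Assumed: equal groups, since one number is given for both, and no dropout, since none is stated.

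**Trying to reproduce 26 per group.**

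- Normal approximation: n = 2 × (1.960 + 0.842)² × (18/20)² = 12.72, so 13 per group and 26 in total.
- Two-sample t-test (noncentral t): n = 13.75, so 14 per group and 28 in total.

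Neither gives 26 per group.

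**Power for 20° with SD 18°.**

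| Per group | t-test | Normal approximation |
|---|---|---|
| 13 | 77.6% | 80.9% |
| 14 | 80.8% | 83.6% |
| 26 | 97.5% | 98.0% |

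At 26 per group the t-test reaches 80% power for a difference of 14.26°, about 14.3°.

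**Could one unstated adjustment explain 26?** Each is applied alone, at 80% power unless noted.

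- Mann-Whitney fallback, by relative efficiency: 13.75/0.955 = 14.4, so 15 (normal data). At the lower bound of 0.864, 13.75/0.864 = 15.9, so 16, or 14/0.864 = 16.2, so 17.
- Alpha 0.025 (split over cup and stem): 15.4 normal or 16.7 t-test, so 16 or 17.
- Alpha 0.0125 (four-way split): 18.06 or 19.7, so 19 or 20.
- 90% power: 17.02 or 18.04, so 18 or 19.
- 95% power: 21.05 or 22.06, so 22 or 23.
- Dropout: turning 14 into 26 needs 1 − 14/26 = 46%; turning 13 into 26 needs 1 − 13/26 = 50%.

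**What does give 26?**

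- The two-group total by the normal approximation: 2 × 13 = 26.
- A t-test at a standardised effect of 0.80, the low end of the range quoted from earlier trials: 25.52, so 26 per group. With SD 18° that is a difference of 0.80 × 18 = 14.4°, not 20°.

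**What the enrolled number supports.** If the 101 students split about 50/51 (1:1 is an assumption), the t-test has 80% power for about 10.1° in cup angle with SD 18°. An SD estimated from ten values is imprecise. Assuming normality, its 95% interval runs from 18 × √(9/19.02) = 12.4° to 18 × √(9/2.70) = 32.9°. The detectable difference then runs from 7.0° to 18.5°.

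**The case against.** The strongest reply is that the number may be right and the inputs wrong. An effect size of 0.80 appears in the same section and gives exactly 26 per group by t-test, so the per-group label could be correct. On that view, telling the authors to write 13 or 14 would replace the planned size with one never planned. It stands that this source is possible and should be named beside 2 × 13, which itself works only with the normal approximation. It does not rescue the text: the section sets the earlier trials aside and says the size rests on its own ten measurements, and 20° with SD 18° is 1.11, not 0.80. If 0.80 was used, an input is misreported.

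A second reply is that adjustments combined can reach 26. For example, alpha 0.0125 with Mann-Whitney efficiency 0.955 and 20% dropout gives 19.7/0.955/0.80 = 25.8. That is true, so the claim that the usual adjustments fall short holds only for each taken singly. No such combination is stated.

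A third reply is that *its group* may have been meant as a total. Then the normal-approximation arithmetic is right and the wording is wrong, so the sentence still needs correcting. By the SAP's t-test, 26 in total gives 77.6% power, slightly under the target.

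Finally, the discrepancy is conservative and nothing in the SAP depends on 26. That is accepted and is why the point is minor.

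**Conclusion.** The concern holds. As written, the sample size does not follow from its inputs: 26 per group is stated, against 13 or 14 computed, so the stated figure is 26/13 = 2.0 or 26/14 = 1.9 times what is needed. Confidence is high that the sentence is wrong as printed. Whether the label or an input is at fault cannot be settled from the documents. The conclusion rests on reading *its* as *each*, on equal groups, and on no unstated inflation. It takes no view on whether 20°, or an SD from ten measurements, was a sound planning choice. The severity is minor.

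**What to change.** Reword the one sentence in the Power Analysis section.

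- If the printed inputs are the ones used, give 13 per group (26 in total, normal approximation) or 14 per group (28 in total, t-test), and name the formula.
- If 26 per group was really the result, report the difference, SD, alpha, power and any adjustment used when it was calculated. An effect size should not be chosen afterwards to match 26.
- In either case, replace *its group* with *each group* or *in total*.

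Optionally, add the difference detectable with the 101 enrolled (about 10.1° with SD 18°, or 7.0° to 18.5° over the interval for the SD), labelled with its assumptions.

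The cost is one sentence, with no extra participants and no change to the analysis.

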**Figure 1, Study Design**

### **Statistical Analysis Plan (SAP)**

The primary outcome was the mean implanted cup inclination and femoral stem anteversion difference between the VR and control groups. Other outcomes considered between groups included: a) the duration required to complete the task, b) the frequency of requesting assistance, and c) the number of errors made.

We used standard statistical methods to gather descriptive statistics. We conducted the Kolmogorov-Smirnov and Shapiro-Wilk tests to check whether the data followed a normal distribution. Our statistical tests were two-tailed, and we set the alpha level at 0.05. For continuous variables that were normally distributed, we used the two-sided independent sample t-test, while for those that weren't normally distributed, we used the Mann-Whitney U-test. We compared categorical data using the chi-square test. To determine if using VR had an impact on a student's task performance, a paired t-test was conducted to compare their outcomes with and without VR. We performed all statistical analyses using SPSS software (IBM, version 27.0).

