## Objectives

This prospective randomised trial aims to test if Virtual Reality (VR) simulation helps medical students who have no surgical experience acquire basic surgical skills in total hip arthroplasty (THA) by performing two difficult THA steps: the acetabular cup and femoral stem implantation in a specific position. This study hypothesised that VR training could help young doctors orient themselves in space and perform more accurate cup implantation in 60° inclination and femoral stem in 20° anteversion than a control group that had only video teaching from an expert. The primary outcome will be the a. the difference in the mean implanted cup inclination and femoral stem anteversion between the VR and control group b. the mean difference between the asked predefined and the actual implanted cup inclination or cup version between the VR and control groups. Secondary outcomes will be other differences in completing the task between groups a. the time needed to complete the task and b. the times asking for assistance c. the number of mistakes.

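### The SAP's primary outcome compares mean angles and omits deviation from the requested angle, so it does not test the accuracy hypothesis

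*Combined protocol and SAP*

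**What the plan says.** The Objectives section frames the hypothesis as accuracy: VR-trained students should "perform more accurate cup implantation in 60° inclination and femoral stem in 20° anteversion". The Saw bone simulation section sets the matching task: "all participants were asked to implant the cup at a 60° inclination in sawbones and the femoral stem at 20° of anteversion".

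The Objectives then give two primary outcomes: (a) the between-group difference in mean cup inclination and mean stem anteversion, and (b) "the mean difference between the asked predefined and the actual implanted cup inclination or cup version between the VR and control groups".

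The SAP keeps only (a): "The primary outcome was the mean implanted cup inclination and femoral stem anteversion difference between the VR and control groups". Its other outcomes are task time, requests for help and errors. Deviation from the requested angle is in neither SAP list. On error control the SAP says only "Our statistical tests were two-tailed, and we set the alpha level at 0.05".

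The Power Analysis section is also on the raw-angle scale. Among the first ten cup placements "the mean cup angle was 50.40 with a standard deviation of 18" degrees, and the calculation is made "To detect a difference of 20 degrees of implantation" between the groups.

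**The concern.** Accuracy means closeness to a target, and a comparison of group means does not use the target. Overshoots and undershoots cancel within a group, so a group scattered widely around 60° has the same mean as one that is consistently right. Conversely, a shift past the target counts as an effect even if students end up just as far from it on the other side.

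Restoring outcome (b) as worded would not repair this. It does not say whether the deviation is signed or absolute, and it names cup inclination or cup version but not the stem.

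At stake is the trial's main conclusion. Followed as written, the SAP could report no benefit when VR makes students more accurate, or a significant difference when it does not.

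A secondary point is that cup and stem are both primary at an unadjusted 0.05, with no statement of whether one or both must be positive.

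**Working it through.** **The plan's own figure.** For a 20° difference, SD 18°, two-sided 0.05 and 80% power: n = 2 × (1.96 + 0.8416)² × 18² / 20² = 12.7, so 13 per group (14 by the exact t-test). The stated 26 fits the total of two groups, not the number per group. That is a separate matter. What counts here is that the calculation concerns a raw angle difference.

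**A signed (b) is the same test as (a).** With a fixed target T, mean(VR − T) − mean(control − T) = mean(VR) − mean(control). T cancels and the SDs are unchanged, so the t statistic is identical.

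**Inputs for the illustration.**
- Target 60° (Saw bone simulation).
- Starting values 50.4° and SD 18° (Power Analysis, which does not say which group they came from).
- 101 students enrolled (Recruitment), taken as 51 v 50; the ratio is assumed.
- Normal angles: assumed.
- All second-group values are assumed, except that row 3 adds the plan's own 20°. Row 1 also assumes its first-group mean of 60°.

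**Mean absolute error** (folded normal, b = |mean − 60|, s = SD): E = s√(2/π)·exp(−b²/2s²) + b·[1 − 2Φ(−b/s)].
- 50.4°, SD 18° (b = 9.6): 14.36 × 0.867 + 9.6 × 0.406 = 16.4°.
- 70.4°, SD 18° (b = 10.4): 14.36 × 0.846 + 10.4 × 0.437 = 16.7°.
- 60° (b = 0): 0.798 × SD, that is 14.4° at SD 18° and 7.2° at SD 9°.

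**Rejection rates** at two-sided 0.05, 20,000 simulated trials per row:

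| | Group 1 v group 2 (mean/SD) | Mean absolute error | t-test, raw angle | Mann-Whitney, absolute deviation |
|---|---|---|---|---|
| 1 | 60/18 v 60/9 | 14.4° v 7.2° | 5% | 96% |
| 2 | 50.4/18 v 55/12 | 16.4° v 10.4° | 32% | 70% |
| 3 | 50.4/18 v 70.4/18 | 16.4° v 16.7° | >99.9% | 5% |
| 4 | 50.4/18 v 60/12 | 16.4° v 9.6° | 88% | 83% |
| 5 | 50.4/18 v 60/18 | 16.4° v 14.4° | 76% | 11% |

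Rows 1 and 2 are real gains that the raw test misses wholly or mostly. Row 3 is no gain, yet the raw test is almost always significant (97.5% at the planned 26 per group). Row 4 shows where the raw test works. Row 5 shows what absolute deviation gives up. With a t-test on absolute deviation, row 1 becomes 99%, row 2 84% and row 5 14%.

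**Worse accuracy can also be significant.** With VR at 40° and control at 60°, both SD 18°, error is 22.4° v 14.4°, and the raw test rejects in about 97.6% of trials at 26 per group.

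**The paired t-test does not fill the gap.** The SAP names no outcome for it, and each student's placements with and without VR are different tasks, with targets of 60° and 20°.

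**Two primary components.** If either alone counts as success and the tests are independent, the false-positive chance is 1 − 0.95² = 9.75%.

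**The case against.** Protocol and SAP are one document. The Objectives still list (b) as primary, the SAP never withdraws it, and its general rule for continuous variables could be applied to it. On that reading the fault is only an inconsistency. This does not rescue the plan: a signed (b) adds nothing to (a), and (b) leaves out the stem.

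The scenarios rest on assumed values. No document gives an SD of 9° or 12°, or any VR mean, and row 3 further assumes that the pilot mean represents controls and that the 20° shift is upward. A reader who saw 70.4° against a 60° target would also notice the overshoot. This stands as a limit: the figures show what can happen, not how likely it is. Row 1 is the harder case, because the group means would not reveal the gain.

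Three further points stand but are peripheral:
- All figures are for the cup; the documents give no mean or SD for the stem.
- The SAP names both Kolmogorov-Smirnov and Shapiro-Wilk without saying which governs. In simulation Shapiro-Wilk rejected normality of the absolute deviations in at least one group in over 99% of trials in rows 1 to 4, but Kolmogorov-Smirnov (Lilliefors form) in only about 79% to 85%. The choice between t-test and Mann-Whitney is therefore not settled.
- Multiplicity is a side issue, and 9.75% applies only if either component suffices.

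Finally, squared error or the proportion within a tolerance would also measure accuracy. Absolute deviation is the simplest choice, not the only one.

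**Conclusion.** The concern holds: the SAP's primary outcome is wrong as written for the stated hypothesis. The omission is plain from the text, and the blindness of a mean comparison to the target does not depend on any assumed value. The size does. For the cup, with normal angles and 51 v 50 students, the raw test ranges from about 5% rejection when error is halved to over 99.9% when there is no gain. It remains informative when VR both moves the mean onto the target and narrows the spread (88%), but the SAP as written cannot separate that case from the misleading ones. The same logic applies to the stem, where the documents allow no figures. This should be corrected before the primary result is interpreted.

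**What to change.** **Change, in both the Objectives and the SAP**
- Define the primary outcome as |achieved − requested angle| for cup inclination (60°) and stem anteversion (20°), compared between VR and control. Replace the reference to cup version.
- Name the test in advance: Mann-Whitney is the natural choice for a skewed deviation.
- Keep the raw mean angle as a secondary outcome, to show the direction of any bias.
- Test the two components by Holm at a familywise 0.05, or name one as the single primary.
- State the detectable difference in absolute error.
- If outcome data have already been seen, label the change post hoc and report the planned mean-angle result beside it. Recruitment through the SAP is mostly written in the past tense, so this may apply.

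**Cost**
- No new measurements: the angles are already recorded.
- Less power for a pure shift of the mean (row 5: 76% falls to 11%), although that shift improves accuracy by only 16.4 − 14.4 = 2.0°.
- The existing sample size does not cover the new outcome. Absolute deviations at 50.4°/SD 18° have SD √(18² + 9.6² − 16.36²) = 12.2°. At 51 v 50 and 80% power, the t-test with equal SDs detects 0.563 × 12.2 = 6.9° at 0.05 and 0.621 × 12.2 = 7.6° at Holm's first step of 0.025. Mann-Whitney, with bias and spread shrunk in proportion, detects about 6.6° and 7.2°.
- A 5° gain needs about 95 per group by t-test with equal SDs, or about 100 by Mann-Whitney under proportional shrinkage. That is roughly twice what 101 students provide.
- These figures are for the cup only; the stem needs its own SD.

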#### VR training

As mentioned, each participant was randomised and did one implantation, either the acetabular cup or the femoral stem, following VR training and the other (stem or cup) without VR training, respectively. This method allowed us to evaluate and compare the performance of participants who received VR training versus those who did not within the same implantation. It also enables us to assess individual participants' performance in both scenarios (stem or cup), with and without VR training.

Before the VR-THA training, participants were asked to complete a survey evaluating their previous VR technology experience. All VR group participants were then asked to complete three consecutive VR sessions using the VR system (ORama VR, Geneva, Switzerland), performing cup or stem implantation based on their group.

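### Cup and stem are both primary and each is tested at 0.05 with no success rule; if either result alone may support the single aim, the chance of a false positive is about 8–10%

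*Combined protocol and SAP*

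**What the plan says.** The SAP states: "The primary outcome was the mean implanted cup inclination and femoral stem anteversion difference between the VR and control groups". Cup and stem are different angles on different implants, and a student who is in the VR group for one is a control for the other (Randomisation), so this sentence implies two tests. Each is an independent-samples t-test, or a Mann-Whitney test if the data are not normal. The level is common to all tests: "Our statistical tests were two-tailed, and we set the alpha level at 0.05". No success rule, order of testing, alpha split or adjustment is given.

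Three other places bear on how the two results would be used:
- The Objectives state one overall aim: the trial "aims to test if Virtual Reality (VR) simulation helps medical students who have no surgical experience acquire basic surgical skills". The hypothesis joins the two components: students would "perform more accurate cup implantation in 60° inclination and femoral stem in 20° anteversion than a control group".
- The VR training section says that the design allows the investigators to "compare the performance of participants who received VR training versus those who did not within the same implantation".
- The Objectives list a second primary outcome, (b): "the mean difference between the asked predefined and the actual implanted cup inclination or cup version between the VR and control groups". The SAP does not carry it over.

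The Power Analysis covers the cup only, at two-sided 0.05. The SAP also plans a paired t-test within students, with no stated primary or secondary status.

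**The concern.** A 5% level per test holds the error of each test, not of a conclusion that either test can trigger. The aim is a single statement about VR training, and two tests could each be taken as supporting it. Whether they may is not written down.

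The wording can be read in more than one way. The *and* in the hypothesis can mean that both components must succeed. The comparison within each implantation can mean two separate claims. The single aim can mean that either result suffices. These readings have different error rates and different power. With nothing stated, the choice could be made once it is known which component was significant.

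**Working it through.** **Plan's own figure.** The plan gives no overall error rate to reproduce, only 0.05 per test. Its one sample size, 26 per group for the cup, does not enter the error calculation. Whether it follows from its inputs is a separate issue.

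**Inputs from the documents.** Two primary components and two-sided alpha 0.05 (SAP); 101 students (Recruitment); SD 18° and a 20° difference for the cup (Power Analysis); swapped arms (Randomisation).

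**Assumptions.** The documents do not give the within-student correlation between cup and stem angles, the split between arms or the stem SD. I took correlations of 0 to 0.7, with 0.9 as an extreme, and splits of 50/51 and 40/61. Data are normal and tests are t-tests on raw angles.

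**1. Either result suffices.** For independent tests: 1 − 0.95² = 0.0975. For correlated tests the error is 1 − P(|Z₁| < 1.96 and |Z₂| < 1.96), with Z₁ and Z₂ bivariate normal. Swapping arms reverses the sign of the correlation, which does not matter for two-sided tests. The simulation used 100,000 runs of the swapped design with no true effect.

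| Correlation | Bivariate normal | Simulated 50/51 | Simulated 40/61 |
|---|---|---|---|
| 0 | 9.75% | 9.74% | 9.69% |
| 0.3 | 9.51% | 9.43% | 9.49% |
| 0.5 | 9.07% | 9.10% | 9.06% |
| 0.7 | 8.35% | 8.25% | 8.45% |
| 0.9 | 7.04% | – | – |

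**2. Outcome (b) also primary.** If (b) is read as covering both cup and stem, there are four tests. If any one suffices and they are independent, the error is 1 − 0.95⁴ = 18.5%. Simulation under assumed distributions gave about 15–18%.

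**3. Both required, each in favour of VR.** If at least one component has no effect, the joint rule cannot succeed falsely more often than that component's own one-sided rate, 0.025, whatever the correlation.
- Only the cup has an effect (20°): about 2.5%.
- Neither has an effect: 0.025² = 0.06% if independent. In simulation (50/51) it was 0.06, 0.006, 0.001 and 0% at correlations 0, 0.3, 0.5 and 0.7. It falls because swapped arms make the two VR-minus-control statistics negatively correlated. This takes the favourable direction to have the same sign for both components.

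Counting double significance in *any* direction gives 0.2–1.7% and about 5% in these two situations. Those figures include results that favour VR on one component and control on the other, so they do not describe this rule.

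**4. Holm.** With no effect in either component, the error is that of two tests at 0.025: 1 − 0.975² = 4.94% if independent, and 4.3–4.9% in simulation. If one component has a true effect, the other is tested at 0.05 at most. The overall error is therefore at or below 5%.

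**5. Cost in power.** The detectable cup difference at 80% power is roughly (z₁₋α/₂ + 0.842) × 18 × √(1/50 + 1/51), where the last two factors give 3.58°.
- Alpha 0.05: 2.802 × 3.58 ≈ 10.0°; exact noncentral t, 10.1°.
- Alpha 0.025: 3.083 × 3.58 ≈ 11.0°; exact, 11.2°.
- Split 40/61: 10.4° and 11.4°.
- Power for 20°: 0.9998, then 0.9995 (50/51).

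If both are required and each alone has 80% power, joint power is 0.8² = 64% when independent, and 60–64% for correlations 0 to 0.7. If the cup difference is 20°, joint power is practically the stem's own power: 32%, 70% or 98% for assumed stem effects of 0.3, 0.5 or 0.8 SD.

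**The case against.** The strongest reply is that there may be no inflation at all. Read literally, the *and* in the hypothesis requires both components. Read through the VR training section, cup and stem are two questions, each held at 5%. Whether two separate claims in one trial need joint control is partly a matter of judgement. This stands. A reader might infer that the trial runs at a false-positive rate near 10%, or even 18.5%, but the documents do not support that: nowhere do they say that either result suffices, and they do not settle the status of outcome (b). What remains is that a hypothesis worded with *and* is not a decision rule, and that the single aim leaves the either-suffices use open.

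It is also fair to object that favouring VR has no direction for a raw mean angle. The targets are 60° and 20°, so a higher or lower mean is not better in itself. The first ten cup measurements averaged 50.4°, and no stem mean is given. A joint rule therefore needs more than one added sentence.

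Finally, much of the text is in the past tense, and the Power Analysis uses this study's own measurements. If results have been seen, a rule added now cannot restore error control. That limits the benefit of the change but is no reason to leave the rule unstated.

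**Conclusion.** The concern holds conditionally. The plan has two primary comparisons at 0.05 each and no success rule.
- **Either may support the overall aim:** the error is 9.75% if the tests are independent, about 8–10% for an assumed correlation of 0 to 0.7, and about 7% at 0.9. It is higher if outcome (b) also counts.
- **Both required, or separate claims only with no overall claim:** 5% is not exceeded for the claims made. Requiring both in favour of VR gives below 0.1% when neither component has an effect and about 2.5% when only one has.

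The figures rest on normal data, t-tests on raw angles and the assumed correlations and splits. Stem power cannot be computed, because no stem SD is given. The change is worth making because it closes a choice that could otherwise follow the results.

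**What to change.** 1. Choose one primary variable per component and use it in both the Objectives and the SAP. Label the other version and the paired t-test secondary.
2. Name cup and stem as the two primary comparisons and test them with Holm: the smaller p-value at 0.025 and, if that is significant, the other at 0.05. This still allows separate cup and stem claims. If Holm is chosen, use alpha 0.025 in the power paragraph.
3. If a joint claim is intended instead, state that both must be significant at 0.05, and define what favours VR relative to the 60° and 20° targets.
4. If results had already been seen, label the rule as added afterwards.

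The cost in text is a few sentences. Under Holm, a lone p-value between 0.025 and 0.05 no longer supports a claim. The rise of about 1° in the detectable cup difference is the worst case, since the cup is tested at 0.05 whenever the stem passes at 0.025. Under the joint rule alpha stays at 0.05, but success depends on the stem as well, and joint power is lower than the power for either component alone.
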